2.1.4.2.7 Time elapsed below LOQ of parasitemia

The time elapsed below Limit of Quantification parasitemia (LOQ expressed in parasites/ μ L will be determined once the assay is validated) is the time for which no parasites are seen i.e time corresponding to PCT up to the time of occurrence of a new malaria infection or recrudescence. If there is no occurrence of new malaria infection or recrudescence, this is the time corresponding to first negative thick film up to the end of study.

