7.7.1 Rescue medicine

The study site will supply rescue medication that will be obtained locally upon local recommendation.

The use of established anti-malarial drug combination per WHO recommendations (6) and per local regulations and the choice of the best therapeutic option is left at investigator's decision.

The use of rescue medications is allowed as soon as

- vomiting occurs during FQ dosing or after FQ dosing but before OZ439 administration,
- vomiting occurs within 35 minutes after OZ439 re-dosing (see Section 7.1.1.2), or
- there is evidence of treatment failure (see definition below).

If no rescue medication is administered before Day 28, it will be administered on Day 28.

Treatment failure is defined according to WHO recommendations (2) as follows:

Early treatment failure (one the following)

- danger signs or severe malaria on Day 1, 2, or 3 in the presence of parasitemia;
- parasite count on Day 2 higher than on Day 0, irrespective of axillary temperature;
- parasitemia on Day 3 with axillary temperature ≥ 37.5 °C;
- parasite count on Day $3 \ge 25\%$ on Day 0.

Late clinical failure

- danger signs or severe malaria on any day between Day 4 and Day 28 in the presence of parasitemia, without previously meeting any of the criteria of early treatment failure;
- presence of parasitemia and axillary temperature ≥37.5°C (or history of fever) on any day between Day 4 and Day 28, without previously meeting any of the criteria of early treatment failure.

Late parasitological failure

• presence of parasitemia on any day between Day 7 and Day 28 and axillary temperature <37.5°C, without previously meeting any of the criteria of early treatment failure or late clinical failure.

Before giving a rescue therapy before Day 28, where possible:

- a PK (OZ439 and FQ) sample should be taken
- blood films, parasite genotyping, RT-qPCR, and qPCR must be taken

Following administration of rescue therapy before Day 28, patients should be managed according to local standard of care practices. Safety data, parasitemia (blood films), and PK data should continue to be collected in the e-CRF, according to the study schedule, and up to the end of the study (Day 28) even if re-emergence is confirmed.

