Recrudescence: The appearance of asexual parasites after clearance of initial infection with a genotype identical to that of parasites present at baseline. Recrudescence is confirmed by microscopy (positive blood smear) and by genotyping PCR analysis.

Re-infection: The appearance of asexual parasites after clearance of initial infection with a genotype that differs from that of parasites present at baseline. Re-infection is confirmed by microscopy (positive blood smear) and by genotyping PCR analysis.

Treatment failure: Any patients who met any of the criteria for ETF, LCF or LPF.

Crude ACPR does not distinguish between re-infection (by a new clone of parasite) and recrudescence (re-emergence of the original clone of parasite that was present at baseline); i.e. presence of either a new clone or genotypically identical parasite will be considered a treatment failure.

PCR-corrected ACPR applies only to recrudescence; (i.e. patients with re-infection are considered non-evaluable for the analysis of PCR-adjusted ACPR). Presence of a genotypically identical parasite will be considered a treatment failure.

Genotyping adjustment

LCF occurring from Day 7 or LPF will be sub-classified as follows using parasite genotyping results:

- *P. falciparum* recrudescence, if no other species reported in eCRF and genotyping result is “recrudescence”
- *P. falciparum* reinfection, if no other species reported in eCRF and genotyping result is “reinfection”

- Other species with *P. falciparum* recrudescence, if other species reported in eCRF and genotyping result is “recrudescence”
- Other species with *P. falciparum* reinfection, if other species reported in eCRF and genotyping result is “reinfection”
- Undetermined, negative or missing PCR, if genotyping result is “Undetermined”, “negative”, “undetermined” or “missing”, with or without other species infection.

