2.1.4.2.3 Parasite clearance time (PCT)

For a conservative approach, parasite clearance should not be claimed based on negative parasitemia obtained by imputation. Therefore, in this section **no imputation of missing parasitemia** will be used, except in case of concomitant fever where the missing parasitemia will be considered as positive.

Timing to consider

In this section, except otherwise specified, the post-dose timing associated to a parasitemia will refer to:

- its assigned time point as defined in [Section 2.5.4.1](#), if it exists,
- its actual post-dose timing as defined in [Section 2.5.4](#) and expressed in hours, if outside defined time windows. None or very few are expected, otherwise it should be taken into account in the analyses.

Establishing the clearance

A blood thick film is considered negative when asexual forms of *P. falciparum* are reported as absent on the dedicated e-CRF page, even if other species are reported.

The parasite clearance will be concluded as soon as two consecutive thick films are negative, with second film prepared within 6 to 12 hours of the first (actual times). In case, the second film has been performed less than 6 hours or greater than 12 hours of the first, then the parasite clearance will be confirmed or invalidated by the thick film following the second one, whatever the timing of this third film:

- If this third film is negative, then the clearance is confirmed.
- If this third film is positive, then the clearance is invalidated.

Time to parasite clearance

When the parasite clearance is confirmed, the time to parasite clearance is the post-dose timing associated to the first negative thick film, as defined above.

In case the parasite clearance is not observed or confirmed before withdrawn (for any reason) or before start of rescue therapy, then the time to parasite clearance will be censored at the time of the last blood film (using the post-dose timing above defined) before withdrawn or rescue therapy start, whichever comes first. Blood films (including date and time of recording) performed the day of rescue start are regarded as before rescue.

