2.3.2 Efficacy populations

2.3.2.1 *Modified Intent-to-treat population*

The modified intent-to-treat (mITT) population includes all randomized patients who received the single administration of IMP, with parasitologically confirmed *P. falciparum* malaria at baseline, having parasitemia data post-randomization.

For analyses and displays, patients will be classified according to the randomized treatment regardless of actual treatment received.

2.3.2.2 *Per-protocol population*

The per-protocol (PP) is the population receiving at least the single administration of FQ 400mg/OZ439, with parasitologically confirmed malaria at baseline, having parasitemia data post-randomization in order to be evaluable for Day 28 ACPR, without major protocol violations possibly affecting efficacy outcome. Note PCR-corrected ACPR applies only to recrudescence i.e. patients with new infections are considered non-evaluable for the analysis of PCR-corrected ACPR see Section 2.1.4).

Parasitemia data for patients with rescue treatment started before the considered time point will be excluded from this time point until Day 28.

In case of vomiting or other reasons interrupting the administration of the complete dose, and if valid parasitemia data post-randomization available, then patients will be included in the PP population.

As defined in [Section 2.1.4.1](#), there are certain criteria that would exclude patients from having an evaluable PCR-corrected ACPR at Day 28:

- Other species infection without *P. falciparum* reemergence,
- Lost to follow-up,
- Withdrawal,
- Protocol violation.

Protocol violations considered above are those potentially impacting efficacy assessments at Day 28:

- Patients who did not take IMP or who needed rescue treatment due to vomiting during IMP administration. Start of vomiting will be classified in 3 categories (< 5 minutes, [5-35] minutes, > 35 minutes and < 6 hours).
- Patient presenting severe malaria or receiving a rescue treatment due to severe malaria during the first 24 hours following IMP start (i.e. wrong inclusion).
- Start of rescue therapy before Day 28 assessment not due to: vomiting during IMP administration, wrong inclusion, treatment failure (per investigator or per WHO criteria), or other species infections.
- Missing baseline parasitemia, and positive parasitemia at 48 or 72 hours.
- Intermittent missing or out of window post-baseline parasitemia preventing to evaluate ACPR Day 28.

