2.4.4.2.10 Elapsed time below LOQ of parasitemia

Same analyses than those described in [Section 2.4.4.2.7](#) for time to re-emergence. All subjects within the associated population will be included.

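### SAP 2.1.4.2.7 gives time below the LOQ of parasitemia no stop at rescue or withdrawal, so parasite-free time after rescue is either credited to study drug or left undefined

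*SAP*

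**What the plan says.** SAP 2.1.4.2.7 defines this secondary endpoint in two sentences. With a recurrence, the interval is the "time corresponding to PCT up to the time of occurrence of a new malaria infection or recrudescence". Without one, "this is the time corresponding to first negative thick film up to the end of study". Neither sentence mentions rescue, withdrawal or loss to follow-up, or says whether the end counts as an event or a censoring.

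The surrounding text bears on this as follows.

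- **Recurrence needs earlier clearance.** SAP 2.1.4 defines recrudescence as "The appearance of asexual parasites after clearance of initial infection with a genotype identical to that of parasites present at baseline". Reinfection carries the same condition.
- **Rescue can come before clearance.** One early-failure criterion in Protocol 7.7.1 is "parasite count on Day 2 higher than on Day 0, irrespective of axillary temperature". After rescue, "Safety data, parasitemia (blood films), and PK data should continue to be collected in the e-CRF", up to Day 28. Participants not rescued earlier all receive rescue on Day 28.
- **Neighbouring endpoints deal with rescue.** If clearance is not observed or confirmed before rescue or withdrawal, "then the time to parasite clearance will be censored at the time of the last blood film" before whichever comes first (2.1.4.2.3). Re-emergence time is zero for a patient who never cleared. For one who cleared and was rescued without recurrence, it is an event at rescue start, or censored there if the case is a protocol violation (2.1.4.2.4). Fever clearance is censored at rescue (2.1.4.2.8). The parasitemia summaries omit post-rescue assessments (2.4.4.2.2).
- **The general exclusion is tied to other populations.** The rule "Parasitemia data for patients with rescue treatment started before the considered time point will be excluded" stands in the per-protocol definition (2.3.2.2) and again in the PK/PD efficacy definition (2.3.5.1). The mITT definition (2.3.2.1) does not contain it.
- **The population is stated two ways.** SAP 2.4.4.2 puts this endpoint on mITT only. The summary table at the end of Appendix B lists PP.
- **Analysis.** SAP 2.4.4.2.10 takes over the Kaplan-Meier analysis planned for re-emergence and adds: "All subjects within the associated population will be included".

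**The concern.** Parasite-free time after rescue reflects the rescue drug. An endpoint used to evaluate the dose-response of OZ439 should not count it. Two kinds of patient fall into the gap:

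1. Those rescued before clearing, who then clear on the rescue drug. They cannot have a recrudescence of the treated episode before that, so nothing in 2.1.4.2.7 stops their clock.
2. Those who clear on study drug and are then rescued without recurrence. SAP Table 1 foresees rescue by investigator decision without the WHO criteria.

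Both can end up with values close to a cure. Patients who withdraw or are lost also have no stated stop. In addition, Protocol 5.3 defines the end of the study as the last visit of the last participant, so the end point in 2.1.4.2.7 is not literally the participant's own Day 28.

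**Working it through.** The plan states no figure for this endpoint, and no sample-size figure depends on it, so there is nothing to reproduce. The check applies 2.1.4.2.7 to example patients.

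**Inputs.** Follow-up ends on Day 28 (Protocol 5.3). Early failure is declared on Days 1 to 3 (Protocol 7.7.1). The days of first negative film, rescue and recrudescence below are assumptions; the documents give none.

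**Formula, literal reading.** Without recurrence: days credited = 28 − day of first negative film. With recurrence: days credited = day of recurrence − day of first negative film.

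| Patient (assumed times) | 2.1.4.2.7 read literally | With the rescue rules of 2.1.4.2.4 |
|---|---|---|
| Cure, first negative film Day 1 to 3 | 28 − 1 = 27 to 28 − 3 = 25 | unchanged |
| Rescued Day 2 or 3 before clearing, first negative film Day 3 to 7 | 28 − 3 = 25 to 28 − 7 = 21 | 0 |
| Cleared Day 2, rescued Day 5, no recurrence | 28 − 2 = 26 | 5 − 2 = 3 |
| Cleared Day 2, recrudescence Day 14 | 14 − 2 = 12 | unchanged |
| Cleared Day 2, recrudescence Day 21 | 21 − 2 = 19 | unchanged |

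**Comparison with a cure.** A patient rescued before clearing, with a first negative film on Day 4, gets 24 days. A cure clearing on Day 2 gets 26, and 24/26 = 92%. Over the assumed ranges the ratio runs from 21/27 = 78% to 25/25 = 100%. The same early failure outranks patients who responded and recrudesced on Day 14 or 21.

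**The other reading.** If the interval starts at the parasite clearance time of 2.1.4.2.3, the patient rescued before clearing has only a censored start. The duration is then undefined, while 2.4.4.2.10 requires a value for every subject. The patient cleared on Day 2 and rescued on Day 5 still gets 26 days, because the start is valid and no recurrence stops the clock.

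**Sensitivity for one arm mean, literal reading.** The simulated success rate for FQ alone is 72% (SAP 1.3), so failures are 28%. Let s be the share of failures rescued before clearing, each credited 24 days instead of 0. The overstatement of the mean is 0.28 × s × 24:

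- s = 10%: 0.7 days
- s = 25%: 1.7 days
- s = 50%: 3.4 days
- s = 100%: 6.7 days

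The documents do not give s. These lines show how the result depends on it; they do not estimate the effect.

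**The case against.** The strongest reply is that the SAP can be read so that the gap closes.

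- **Start at the clearance time.** The first sentence of 2.1.4.2.7 starts at PCT, and the first negative film in the second sentence may only restate it. On that reading the 21 to 25 days do not arise. This stands as a fair alternative, but it replaces a wrong value with no value and leaves the cleared-then-rescued patient unchanged.
- **Recrudescence time from 2.1.4.2.5.** That section equates time to recrudescence with time to re-emergence, apart from some cases on or after Day 7, and so takes over the rescue rules of 2.1.4.2.4. If 2.1.4.2.7 takes its stop from there, a cleared patient stops at rescue. But 2.1.4.2.7 makes no such reference, and 2.1.4 defines recrudescence by genotype after clearance. For a patient who never cleared, a stop at time zero before any start still gives no usable duration.
- **PP in the summary table.** PP drops post-rescue parasitemia. This conflicts with mITT in 2.4.4.2. It would not fully help either: a cleared patient rescued as a failure on the investigator's judgement can remain in PP, has no recurrence, and still runs to the end of study.

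A reader might infer two stronger conclusions. One is that a rescued early failure is definitely scored like a cure. This holds only on the literal reading and with the assumed film times. The other is that the OZ439 dose-response is diluted, because failures are expected mostly at low doses. The documents do not establish that. The 28% covers all failures on PCR-corrected ACPR, and recrudescences already stop the clock. For rescues due to vomiting, nothing points to the low-dose arms, and one trigger, vomiting after OZ439 re-dosing, cannot occur with FQ alone. Event or censoring status is also not stated, so how these patients would appear on the Kaplan-Meier curve is itself an inference.

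**Conclusion.** The gap is real. SAP 2.1.4.2.7 contains no stop at rescue or withdrawal, and no general rule supplies one for mITT. A patient who clears and is rescued without recurrence is credited to the end of study under both start points; only an unstated link to 2.1.4.2.5 would prevent this. A patient who first clears after rescue is either credited with rescue-drug time or left undefined. This conflicts with 2.1.4.2.3, 2.1.4.2.4 and 2.1.4.2.8.

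Per affected patient, the excess under the assumed times is about 21 to 25 days for rescue before clearance, and 23 days (26 − 3) in the cleared-then-rescued example. The number of such patients, the effect by arm and its direction cannot be derived from the documents. Late failures with recrudescence or reinfection are handled. The endpoint is secondary; the primary analysis and the sample size are unaffected. The text should be amended before database lock.

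**What to change.** Amend SAP 2.1.4.2.7 as follows.

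1. Use only films up to rescue; films on the day of rescue count as before it, as in 2.1.4.2.3.
2. Set the duration to zero if clearance is not established before rescue. This follows 2.1.4.2.4 rather than the censoring in 2.1.4.2.3, and the SAP should say so.
3. For patients who cleared, end the duration at rescue given before the Day 28 assessment, as event or censored in line with 2.1.4.2.4. For withdrawal or loss to follow-up, censor at the last film before it.
4. State that the systematic Day 28 rescue is not an event. Copying 2.1.4.2.4 unchanged would literally turn every cure into an event on Day 28.
5. Replace the end of study with the participant's own last film up to Day 28.
6. Reconcile mITT in 2.4.4.2 with PP in the summary table for this endpoint.

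The cost is SAP wording and the matching derivation code. No further data are needed. Reported parasite-free time becomes shorter for rescued patients, and arms with more rescue will show it most.

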2.1.4.2.8 Fever clearance time (FCT)

FCT is the time from start of study drug administration until temperature remained below 37.5°C.

Fever is defined by a body temperature $\geq 37.5^{\circ}\text{C}$ for axillary temperature or by a body temperature $\geq 38^{\circ}\text{C}$ for other routes of measurement.

Timing to consider rules will be similar to what it is described in [Section 2.1.4.2.3](#). The FCT is the post-dose timing associated to the first vital sign assessment as defined above.

In case the FCT is not observed or confirmed before withdrawn (for any reason) or before start of rescue therapy, then the FCT will be censored at the time of the last vital sign assessment (using the post-dose timing above defined) before withdrawn or rescue therapy start, whichever comes first.

FCT is not applicable for patients with baseline body temperature $< 37.5^{\circ}\text{C}$ for axillary temperature (or $< 38^{\circ}\text{C}$ for other routes of measurement) or missing.

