- e Local thick and thin blood films performed at the site, before Informed Consent signature, according to local standard procedures and within 4 hours prior to dosing, can be used as screening/ pre-dose parasitemia assessments (Section 9.1.1.1) provided that a standard procedure is in place at site and blood films staining is performed according to the study operational manual. Blood films (thick and thin) and temperature measurements need to be confirmed as follows: when 1st parasite clearance and 1st temperature < 37.5 °C, measurements need to be confirmed with second reading 6 to 12 hours after the first measurement (ie, to determine Parasite Clearance and Fever Clearance). The first measurement (if confirmed) will be considered the 'Clearance Time'. Asexual and sexual counts will be measured separately: only asexual count will be used as parasitemia for evaluation of study endpoints. If parasites have not cleared within 72 hours after IMP administration and criteria for rescue medication are not met at 72 hours post-dose, blood films should continue to be taken according to site standard practice (or at minimum every 8 hours) until parasite clearance is shown or until criteria for rescue medication are met (see Section 7.7.1). If these additional blood smears are taken they should be recorded as unscheduled visits in the e-CRF. Axillary temperature should be recorded, if the axillary method is not possible, an alternative route (oral, tympanic, rectal) may be used. Within an individual participant the same method of temperature measure should be used throughout the study.
- f RT-qPCR and qPCR will be performed at all parasitemia time-points (To be collected, according to the schedule and the instructions reported in the study operational manual). Parasite genotyping analysis will be performed on previously collected blood spot sample only in case of a positive blood film after initial parasite clearance: one pre-dose sample and one sample at 18 or 24 hours post dosing. A further sample will be analyzed at the time point at which recrudescence/re-infection occurs (if applicable).
- q Single local ECG reading for inclusion purpose and triplicate central ECG reading for safety evaluation during study.
- h Laboratory safety will be performed locally: hematology, clinical chemistry, and urinalysis (see Appendix 2 for details).

Clinical Trial Protocol ACT14655 – artefenomel/ferroquine 13-Nov-2017 Version number: 1

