9.4.2 Vital signs

- Axillary temperature, pulse rate, and blood pressure will be assessed.
- Axillary temperature should be recorded in °C and to an accuracy of one decimal place. If the axillary method is not possible, an alternative route (tympanic, oral or rectal) may be used. The alternative route shall be recorded in the e-CRF. Within an individual patient the same method of temperature measurement (axillary, tympanic, oral or rectal) should be used throughout the entire study period.
- Blood pressure and pulse measurements will be assessed with a completely automated device. Manual techniques will be used only if an automated device is not available.
- Blood pressure and pulse measurements should be preceded by at least 5 minutes of rest in supine position for the participant in a quiet setting without distractions (eg, television, cell phones).
- Vital signs (to be taken before blood collection) will consist of 1 pulse and 3 blood pressure measurements (3 consecutive blood pressure readings will be recorded at intervals of at least 1 minute). The average of the 3 blood pressure readings will be recorded on the e-CRF.

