1.6 STATISTICAL MODIFICATIONS MADE IN THE STATISTICAL ANALYSIS PLAN

The primary efficacy population will be the PK/PD population instead of the mITT population stated in the protocol.

A per-protocol [PP] population was added in order to align the analysis population with the primary endpoint of the study. All populations have been further clarified from the protocol definitions

The derivation of the secondary endpoint, Fever clearance time (FCT), has been added. FCT will be assessed by measuring the time from the first dose until the first time that the body temperature dropped and remained <37.5 °C.

Time to 50% parasite reduction (T_{PC50}) will also be calculated in addition to the time to 99% PR.

The evaluation of the relationship between parasitemia (as measured on thick blood film and/or by qPCR) and concentration of OZ439/FQ may be performed in a separate analysis pooling data from different studies and be reported in a separate report.

The terminal half-life ($t_{1/2}$) for OZ439 and ferroquine will not be estimated as this endpoint does not contribute to the objectives of the study.

The definition of baseline to be used for efficacy analyses has been clarified.

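### Fever clearance uses 37.5 °C for every measurement route, although the same SAP section puts the fever limit at 38 °C for non-axillary routes, so some non-axillary clearance times may be delayed or censored

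*SAP*

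**What the plan says.** SAP 2.1.4.2.8 opens with the clearance rule: "FCT is the time from start of study drug administration until temperature remained below 37.5°C". Its next sentence defines fever as 37.5 °C or above "for axillary temperature or by a body temperature $\geq 38^{\circ}\text{C}$ for other routes of measurement". The section closes by making FCT not applicable to anyone whose baseline is missing or below the fever limit for the route used.

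SAP 1.6, which records that FCT was added, repeats the route-free rule: FCT runs "until the first time that the body temperature dropped and remained <37.5 °C". Footnote e of the protocol's schedule of activities, carried into SAP Appendix A, says "when 1st parasite clearance and 1st temperature < 37.5 °C, measurements need to be confirmed with second reading" 6 to 12 hours later. It too gives no route.

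Other routes are allowed. Protocol 9.4.2 states: "If the axillary method is not possible, an alternative route (tympanic, oral or rectal) may be used". It also requires the alternative route to be entered in the e-CRF. Footnote e adds: "Within an individual participant the same method of temperature measure should be used throughout the study".

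Under SAP 2.4.4.2.11, FCT is analysed like time to parasite clearance: descriptive statistics by arm, and Kaplan-Meier estimates by arm and overall. A Cox model is named only in the summary table at the end of SAP Appendix B.

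**The concern.** Entry to the endpoint depends on route and exit does not. By the SAP's own definition a participant with an oral temperature of 37.7 °C has no fever, yet has not cleared it. SAP 2.1.4 cites the same fever definition when deciding whether a missing parasite count is imputed as positive. That participant would therefore be afebrile for the imputation rule and uncleared for FCT.

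At stake are the absolute FCT figures: medians, quartiles and the proportion cleared by a given hour. A participant who lingers between the two limits is given a later time. One who never settles below 37.5 °C is censored at the last assessment before rescue or withdrawal, although no longer febrile under the SAP.

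**Working it through.** The plan gives no figure to reproduce, so the check sets the rules side by side and then applies them to example readings.

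**Rules by route**

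| | Axillary | Oral, tympanic, rectal | Source |
|---|---|---|---|
| Fever | ≥37.5 °C | ≥38 °C | SAP 2.1.4.2.8; also protocol inclusion criterion I 02 and SAP 2.1.2 |
| FCT applies if baseline is | ≥37.5 °C | ≥38 °C | SAP 2.1.4.2.8 |
| Cleared when below | 37.5 °C | 37.5 °C | SAP 2.1.4.2.8, SAP 1.6, footnote e |
| Gap between entry and clearance | 37.5 − 37.5 = 0 °C | 38.0 − 37.5 = 0.5 °C | |

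Temperature is recorded to one decimal place (protocol 9.4.2), so the unclassified band for non-axillary routes is 37.5 to 37.9 °C. No section gives a non-axillary clearance limit or a reason for a stricter one.

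**Direction.** Any reading below 37.5 °C is also below 38 °C. The time from which readings stay below 37.5 °C therefore cannot precede the time from which they stay below 38 °C. The rule as written can delay or censor FCT but cannot shorten it.

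**Two worked non-axillary series.** The documents contain no temperature data, so these values are assumed. Both series stay below 37.5 °C after the last value shown.

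| Hour | 6 | 12 | 18 | 24 | 30 | FCT at 37.5 °C | FCT at 38 °C |
|---|---|---|---|---|---|---|---|
| Series A | 38.4 | 37.8 | 37.7 | 37.6 | 37.4 | 30 h | 12 h |
| Series B | 38.4 | 37.4 | 37.3 | 37.2 | 37.2 | 12 h | 12 h |

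Series A differs by 30 − 12 = 18 h. Series B does not differ, because no reading falls in the band once the temperature is below 38 °C.

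**Sensitivity to assumptions.** A small simulation covered non-axillary patients only. It assumed baseline 38 to 40 °C, settling at 36.8, 37.0 or 37.2 °C, decay half-life 6 or 12 h, reading SD 0.2 or 0.3 °C, and readings from 2 to 168 h.

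- Clearance requiring all later readings to stay below the limit: the two limits gave different FCTs in 77% to 99% of simulated patients. Median FCT was 12 to 120 h at 37.5 °C and 6 to 24 h at 38 °C. Up to 22% had not cleared at 37.5 °C by 168 h.
- Clearance requiring two consecutive readings below the limit: 73% to 97% differed. Medians were 12 to 36 h and 6 to 18 h, and up to 2% had not cleared at 37.5 °C.

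The width of these ranges shows that the inputs drive the answer. They illustrate the mechanism for an affected patient and do not estimate the effect in this trial.

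**The case against.** The best defence is that a uniform, stricter clearance limit may be intended. It appears in SAP 1.6, SAP 2.1.4.2.8 and footnote e, and footnote e is also the note that permits other routes. A clearance limit below the entry limit is not an error in itself, since it guards against declaring clearance too early. But the documents give no such reason, and axillary participants get no such margin. Where the SAP means to be conservative, as for parasite clearance in 2.1.4.2.3, it says so. The defence lowers confidence that this is an oversight; it does not remove the inconsistency.

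It can also be said that the later reference in SAP 2.1.4.2.8 to an assessment defined above imports the fever definition. The explicit 37.5 °C sentence and its repeat in SAP 1.6 tell against that. At best the rule is ambiguous and two programmers could derive different times.

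Three stronger readings are tempting, and the documents do not support them:

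- **That FCT is wrong for every non-axillary participant.** Series B shows it is not.
- **That sites using another route will look slower.** Another route is used only where axillary measurement is not possible, the choice is made per participant, no site is said to use one routinely, and no FCT summary by site is planned.
- **That the comparison of arms is biased.** Temperature is taken at screening, before randomization, and the method should then stay the same. Randomization is stratified by site (SAP 1.1). Route should therefore be balanced across arms in expectation.

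**Conclusion.** The inconsistency is real and minor. For a non-axillary participant with readings of 37.5 to 37.9 °C after falling below 38 °C, FCT as written may be delayed or censored, and never made earlier. All axillary participants, and non-axillary participants who fall directly below 37.5 °C and stay there, have the same FCT under either rule.

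The size in this trial cannot be stated. Axillary is the default, the number measured otherwise is not given, and it may be small or zero. What is affected is the absolute level of FCT, which is not among the protocol's Table 1 endpoints. The primary exposure-response analysis of PCR-corrected ACPR and the sample size do not use it. The expectation of no bias between arms assumes that the method chosen at screening is kept, as footnote e requires.

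**What to change.** In SAP 2.1.4.2.8, define clearance as temperature falling and remaining below the SAP's own fever limit for the route used: 37.5 °C axillary, 38 °C otherwise. Align SAP 1.6. Leave the fever definition as it is, since the imputation rule in SAP 2.1.4 depends on it.

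Footnote e must be reconciled with that definition, because it prompts the confirmatory reading only at the first temperature below 37.5 °C. If only the SAP text changes, a first qualifying non-axillary reading of 37.5 to 37.9 °C would have no prompted confirmation. Where no 6-to-12-hour confirmatory reading exists, the SAP can use the next scheduled reading to confirm that temperature remained below the limit. As I read the schedule's temperature row, that reading comes 6 h later for a first qualifying reading at 6 to 30 h, 12 h later at 36 h (48 − 36), and 24 h later at 48 h (72 − 48). Only from 48 h onward does it miss the 6-to-12-hour window.

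The cost is one extra condition in the derivation, and some non-axillary clearances confirmed by a later scheduled reading. No new data are needed, because the alternative route is already in the e-CRF. The change should be made before database lock.
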